10.2 PATIENT ACCOUNTABILITY AND MISSING DATA

The proportion of subjects with documented follow-up at each interval will be presented descriptively. The number of diagnostic, laboratory, and clinical evaluations will be tabulated by follow-up interval. Also, a listing of patients who initially consent but do not undergo a procedure due to withdrawal of consent prior to procedure will be given. However, these subjects will not be included in any analysis.

Information on missing or withdrawn subjects will be tabulated presenting the number and proportion of subjects eligible for and compliant with each follow-up examination. Subjects who withdraw from the trial will be tabulated with the reasons for the withdrawal. Additional sensitivity analyses will be performed as described below.

The evaluation of subjects with missing data presents a special concern in ITT analyses. All clinical studies analyze the results based on the completed cases (i.e., those who complete the trial). Because missing subjects do not have final data, they present a problem for ITT analyses. The statistical community recommends that multiple sensitivity analyses be conducted to determine the robustness of the result in subjects who complete the study.^{*,†‡§} The intention of these analyses is to demonstrate that the results obtained from the evaluable subjects are not biased.

As a result, sensitivity analyses using multiple imputations will be conducted to evaluate the robustness of the study result accounting for missing observations. The primary effectiveness endpoint analyses will be recalculated using an unbiased imputation of the determination of success or failure. It is expected that the number of subjects with missing effectiveness data at one year will be approximately 10% of study enrollment. The first method of imputation will be to assign values using a simple random sample from the subjects with outcomes at one year. This system is denoted the “Hot Deck by Simple Random Sampling with Replacement”.^{**} The number of subjects to impute is small and trying to

^{*}Pocock S. (1983). Clinical Trials (A Practical Approach). John Wiley and Sons, Chichester.

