[‡]Guidance for Industry: E9 Statistical Principles for Clinical Trials. U. S. Department of Health and Human Services, Food and Drug Administration, Center for Drug Evaluation and Research and Center for Biologics Evaluation and Research. International Committee on Harmonization, September 1998.

[§]Rubin D. Multiple Imputation for Nonresponse in Surveys. 1987: John Wiley and Sons, New York.

^{**}Little R and Rubin D. Statistical Analysis with Missing Data. 2002. John Wiley and Sons, New York.

Confidential. This document and the information contained herein may not be reproduced, used or disclosed without written permission from Endologix, Inc.

provide a more sophisticated imputation method would require modeling missingness with only approximately 10% of enrolling subjects or less with missing data. Additional sensitivity analyses will be done by using other imputation methods; Last Observation Carried Forward (LOCF); subjects lost to follow-up considered an endpoint failure; impute the missing result as having succeeded the endpoint; and impute the missing value by a generating a random number and comparing it to the value of the performance goal for effectiveness.

A comparison of baseline characteristics of the subjects with missing data and those without missing data will be done to determine if there is evidence that the data are not missing at random (it is not possible to determine that data are missing at random). If the missing at random assumption is clearly violated by these comparisons, it is usually possible to find a sub-group that are not missing at random who have to be imputed differently, such as assigning the worst score to subjects in the sub-group. For example, the proportion of subjects missing an outcome may be much greater at a given study site which may also have a higher rate of failure. Those subjects from that site may be assigned a failure and the baseline comparisons of the remaining subjects will be rechecked to see if the imbalances are resolved. If this resolves the missing at random difficulty, the sub groups will be given special scores and the remaining subjects will be imputed as described above. The resolution of the imbalance will be retested by the same methods with the subjects identified above removed.

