10.7 PRIMARY EFFECTIVENESS ANALYSIS

10.7.1 Primary Effectiveness Hypothesis

The primary effectiveness hypothesis is that the Treatment Success rate at one year exceeds a performance goal of 80%. The hypothesis test will be evaluated using the exact binomial distribution as a one-tailed test, using significance level $\alpha=0.05$. Multivariable analyses will be used to assess predictors of success. The null and alternative hypothesis is presented below.

$$H_0: P \leq 0.80 \quad \text{vs.} \quad H_1: P > 0.80$$

Where P is the rate of Treatment Success as defined in §10.7.2.

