10.7.2 Sample Size

The primary trial effectiveness variable is the Treatment Success rate at one year post-operatively. Treatment Success is a composite of clinically-relevant outcomes, including procedural technical success and freedom from: aneurysm rupture; conversion to open repair; Type I endoleak at 12 months; Type III endoleak at 12 months; clinically significant migration; aneurysm sac enlargement; or secondary endovascular procedure up to 12 months for resolution of Type I or III endoleak, device occlusion, migration, aneurysm sac expansion and/or a device defect.

The sample size is obtained by using the exact binomial distribution using PASS 2008. A sample size of 132 subjects at one year in the study population will have 80% power against a null performance goal of 80% if the proportion of Treatment Success is 88% or higher. It is estimated that the rate of Treatment Success will be greater than 88%.

It is anticipated that the drop-out rate of the trial will be 12% or less. Because the larger of the two sample sizes after adjustment for loss to withdrawal is the one for effectiveness, a minimum

of $132/0.88 = 150$ subjects will need to be recruited for this study. Thus to allow for deviations from assumptions, 150 subjects will need to be recruited for this study.

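### The baseline comparison in Section 10.2 checks missing completely at random, not missing at random, and neither the subgroup-failure response nor the marginal hot deck conditions on the variables found imbalanced

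*Combined protocol and SAP*

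**What the plan says.** All of the following is in Section 10.2 unless noted.

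- **Expected missingness.** The plan expects that "the number of subjects with missing effectiveness data at one year will be approximately 10% of study enrollment". Section 10.7.2 allows slightly more: "It is anticipated that the drop-out rate of the trial will be 12% or less".
- **Main imputation.** The first method is "Hot Deck by Simple Random Sampling with Replacement", a draw from everyone with a one-year outcome. The section describes the imputation as unbiased, and says the aim is to show that results in evaluable subjects are not biased. The primary imputation is run 10 times with listed seeds and combined by Rubin's method.
- **Why nothing more elaborate.** The number to impute is small, and a better method is said to need a model for missingness.
- **Diagnostic.** Baseline characteristics are compared between missing and non-missing subjects "to determine if there is evidence that the data are not missing at random". The comparison is treated as able to establish a clear violation of that assumption.
- **Response.** A subgroup may be found that should be imputed differently, for instance with the worst score. In the example, a site has more missing outcomes and perhaps more failures: "Those subjects from that site may be assigned a failure". The comparison is then repeated without those subjects, and the remainder go back to the method above.
- **Other methods.** These are last observation carried forward (LOCF), all missing as failures, all missing as successes, and a random draw against the performance goal.
- **Tipping point.** It is written for MAE, the safety endpoint.

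**The concern.** The diagnostic is attached to the wrong assumption, and that leads to the wrong response. Missing at random means that, given the observed data, missingness does not depend on the unobserved outcome. It permits missingness to vary by site, age or CT finding. A baseline difference is therefore evidence against missing completely at random and says nothing against missing at random. When such a difference is found and the variable predicts outcome, the natural step is to impute within levels of that variable.

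The plan does something else. It offers a failure score for a subgroup chosen after the data are seen, with no stated threshold for a clear violation and no fixed score. Everyone else returns to a draw that ignores the variable. That draw has the completer success rate as its expectation, so agreement with the completer analysis is built in and is no evidence of robustness.

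The rest of the plan makes conditioning natural. Section 10.5 tests the primary endpoints for site heterogeneity at P<0.15 and reweights by site. Section 10.4 flags variables that differ by site as covariates. Section 8.4 schedules CT at 1 and 6 months. The hot deck uses none of this. At stake is whether the lead sensitivity analysis can support a claim against the 80% goal.

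**Working it through.** **The plan's figures.** 132/0.88 = 150, as in Section 10.7.2. Missing outcomes: 10% of 150 = 15, or 12% of 150 = 18. Goal 0.80, alternative 0.88, one-sided alpha 0.05 (Sections 10.7.1 and 10.7.2). The plan gives no figure for the effect of the imputation rule, so its size is illustrated below.

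**Illustration 1: the plan's site example.** From the documents: N = 150, 15 missing, and a largest site of 15% of 150, i.e. 22 subjects (Section 5.1), leaving 128 elsewhere. Assumed: that site holds m = 8 or 10 of the missing, and missingness depends on site only. Let a be the site's true success rate and b the rate elsewhere.

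- Observed successes S = (22−m)a + (128−(15−m))b
- Hot-deck expectation H = S/135
- Site-failure expectation F = [S + (15−m)H]/150
- Truth, and expectation of a site-conditional draw: (22a + 128b)/150

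Worked case, a = 0.50, b = (120−11)/128 = 0.8516, m = 8:

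- S = 14×0.50 + 121×0.8516 = 110.04
- H = 110.04/135 = 0.815
- F = (110.04 + 7×0.8151)/150 = 0.772
- Truth = 0.800

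| a, b | m | Truth | Hot deck (error, points) | Site-failure (error, points) |
|---|---|---|---|---|
| 0.50, 0.852 | 8 | 0.800 | 0.815 (+1.5) | 0.772 (−2.8) |
| 0.50, 0.852 | 10 | 0.800 | 0.820 (+2.0) | 0.766 (−3.4) |
| 0.70, 0.911 | 8 | 0.880 | 0.889 (+0.9) | 0.842 (−3.8) |
| 0.70, 0.911 | 10 | 0.880 | 0.892 (+1.2) | 0.833 (−4.7) |
| 0.88, 0.88 | 8 | 0.880 | 0.880 (0) | 0.833 (−4.7) |
| 0.88, 0.88 | 10 | 0.880 | 0.880 (0) | 0.821 (−5.9) |

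A simulation of 40,000 trials per case, with 10 imputations and Rubin's rules against z = 1.645, gave matching averages (the smallest site-failure error was 2.85 points) and these rejection rates:

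- True rate 0.80: hot deck 13.7% and 17.4% for m = 8 and 10; site-failure 0.4% and 0.1%; site-conditional 6.4% and 6.7%. A full-data normal test gave 4.9%.
- True rate 0.88, site predictive: power 92% and 94% for the hot deck, whose estimate is too high; 40% and 27% for site-failure; 84% and 83% for site-conditional.
- True rate 0.88, site not predictive: power 85% for the hot deck; 28% and 16% for site-failure.

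The last pair of table rows shows that imbalance on a variable unrelated to outcome leaves the hot deck unbiased, while the failure rule still costs most of the power.

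**Illustration 2: dropout related to interim CT.** All inputs except N = 150 and the goal are assumed: true success 0.80; 10% of subjects with an adverse 6-month CT and 30% later success, so the others have (0.80−0.03)/0.90 = 0.8556.

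- Dropout 30% versus 10%: completer rate = (0.07×0.30 + 0.81×0.8556)/0.88 = 0.811
- Dropout 40% versus 9%: completer rate = (0.06×0.30 + 0.819×0.8556)/0.879 = 0.818

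Averaging the exact binomial test over the number of completers gives rejection of 7.6% and 10.5%, against 4.0% when dropout is unrelated to outcome. The marginal hot deck has the same expectation as these completer rates.

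**The case against.** The strongest reply is that Section 10.2 is a set of sensitivity analyses, while Section 10.7.3 tests successes over the number evaluated. Several listed methods do not rely on missing completely at random. This stands, and it rules out four stronger readings.

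- **A reader might infer that the plan never relaxes missing completely at random.** It does. The all-failure and all-success analyses bound every mechanism, the performance-goal draw fixes its own rate, and the subgroup worst score is itself a departure.
- **A reader might infer that interim CT findings are never used.** LOCF may use them. In Illustration 2, if LOCF scores dropouts with an adverse CT as failures and other dropouts as successes, it averages 0.804 and 0.800 and rejects 4.8% and 3.8%. That rests on a scoring rule the plan does not state, and LOCF is a single imputation.
- **A reader might infer repeated testing until imbalance disappears.** The text describes a recheck and no loop.
- **A reader might infer that the failure rule could produce a false positive.** It can only lower success relative to the hot deck. The anti-conservative risk lies in the hot deck.

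Failure is also only an example, so conditional imputation is not excluded. But it is not specified either, and the choice is left until the data are seen.

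The argument from small numbers does not stand. Conditional imputation models the outcome, fitted on the 132 to 135 subjects who have one; no model for missingness is needed.

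**Conclusion.** The point holds in a limited form. The baseline comparison is a check of missing completely at random and cannot show a violation of missing at random. The imputation the plan calls primary does not condition on variables found imbalanced, and the offered remedy is discretionary. Between the extreme bounds there is no covariate- or site-conditional multiple imputation, and effectiveness has no tipping point.

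In the site example the hot deck is 0.9 to 2.0 points high where site predicts outcome and unbiased where it does not. Site-failure is about 2.8 to 5.9 points low throughout, and a site-conditional draw is unbiased. These sizes depend on assumed site success rates, on 8 to 10 of the 15 missing falling at one site, and, in Illustration 2, on assumed CT-related dropout. They show direction and plausible scale and do not forecast the trial's result. The primary test itself is not shown to be wrong. This should be corrected, but it is not a fatal fault.

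**What to change.** In Section 10.2:

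1. Describe the baseline comparison as a check of missing completely at random.
2. Replace the subgroup-failure rule, and the marginal hot deck as primary imputation, with one prespecified conditional imputation: a hot deck within strata, or logistic multiple imputation with 2 to 3 predictors or a penalised fit. Draw the predictors from 30-day and 6-month endoleak, migration and sac status, and from site or baseline variables that both differ by missingness and predict outcome. State the selection rule in advance.
3. Keep the all-failure and all-success analyses.
4. Add a tipping-point analysis for Treatment Success; the existing one covers MAE only.

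The cost is SAP wording and slightly more analysis work on data already collected. The model must stay small because few subjects will be missing, and small sites would need grouping, for which Section 10.4 already has a rule.

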The primary imputation will be done 10 times with 10 different seeds to initiate the random selection and the combined P-value for the 10 imputations will be obtained by a method described in Rubin (1987) and in the SAS manual for PROC MIANALYZE. The seeds to be used for the 10 imputations are selected from a pseudo-random number table in Steele and Torrie (1960) and are 70303, 18191, 62404, 26558, 92804, 15415, 02865, 52449, 78509, and 43896.*

With regard to imputation for the primary safety endpoint, that endpoint is obtained so close to the procedure that there will be very little missing data. If any of the test subjects are lost to follow-up prior to 30 days, that patient will be assigned an MAE for primary analysis purposes.

In addition to the above missing data analyses, Tipping Point analyses will also be performed. For each imputed data set, one MAE will be added and the exact binomial test will be done. The number of steps required to achieve non-significance of the MAE endpoint will be reported for each imputation. The supportive tipping point analysis will be repeated for the completed cases and will be done in the same way by adding one MAE and doing an exact binomial test of the result. The number of steps required to achieve non-significance will be reported for this analysis as well.

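### The tipping-point analysis is defined only for 30-day MAE, where almost nothing is missing, and not for one-year Treatment Success, where about 10% is expected to be missing

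*Combined protocol and SAP*

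**What the plan says.** All the relevant text is in section 10.2.

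- **Effectiveness, extent of missing data.** "It is expected that the number of subjects with missing effectiveness data at one year will be approximately 10% of study enrollment". A later sentence allows for less than that, and section 10.7.2 assumes drop-out of at most 12%.
- **Effectiveness, handling.** "The primary effectiveness endpoint analyses will be recalculated using an unbiased imputation of the determination of success or failure". The main method is a hot deck run with ten seeds, after which "the combined P-value for the 10 imputations will be obtained". The other planned analyses are LOCF, all missing as failures, all missing as successes, and a random draw against the 80% goal. There is also a rule that can assign failures to a subgroup if baseline comparisons clearly contradict missing at random.
- **Safety, extent and handling.** For 30-day MAE the plan says "there will be very little missing data". For anyone lost before 30 days, "that patient will be assigned an MAE for primary analysis purposes".
- **Tipping point.** The opening sentence is general, but the only procedure given is "For each imputed data set, one MAE will be added and the exact binomial test will be done", with the output "The number of steps required to achieve non-significance of the MAE endpoint will be reported for each imputation". Then "The supportive tipping point analysis will be repeated for the completed cases", again by adding one MAE per step.

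The effectiveness analysis plan in section 10.7.3 contains no tipping point. The Revision 03 change table says only that tipping-point analyses were included at FDA request; the request itself is not in the documents.

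**The concern.** A tipping-point analysis asks how unfavourable the unobserved outcomes must be before the conclusion changes. Here it is attached to the endpoint with almost no unobserved outcomes, and those few are already set to the worst value. Nothing missing is left to vary, so the count measures how far the observed MAE rate lies from 56%.

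The reference to imputed data sets does not fit MAE either. The ten-seed imputation is defined for Treatment Success, and the plan does not say how MAE is handled inside those sets. On the natural reading the MAE count is identical in all ten.

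For Treatment Success, missing outcomes can decide the result, yet no planned output states how many missing subjects would have to fail to overturn it.

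**Working it through.** **Inputs.** N=150 recruited, 132 evaluable, drop-out at most 12%, success rates 80% (goal) and 88% (planned), from section 10.7.2. Exact binomial, one-sided 0.05, from section 10.7.3. MAE goal 56%, one-sided 0.025, expected rate 16.6%, from sections 10.6.1 and 10.6.2. About 10% missing at one year, from section 10.2.

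**The plan's own figure.** 132/0.88 = 150, as stated. At 132 evaluable the exact test passes from 114 successes (p=0.038), with 76.7% power at 88%. The smallest n with at least 80% exact power is 135, so the plan's 132 is close; that difference is not at issue here.

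**Threshold in 150 subjects.** P(X≥129 | 150, 0.80) = 0.037 and P(X≥128) = 0.059, so 129 successes are needed. With m missing and x observed successes, significance is lost once the number of missing subjects who fail reaches

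tip = m − (129 − x) + 1.

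For x=116 and m=15: 15 − 13 + 1 = 3. For x=119: 15 − 10 + 1 = 6.

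| Missing | Lowest passing completer result (p) | Tip there | Tip near 88% | Results giving all-failure fails, all-success passes | Share of passing results, true 88% | True 90% |
|---|---|---|---|---|---|---|
| 18 | 114/132 (0.038) | 4 of 18 | 116/132: 6 of 18 | 114–128 | >99.9% | 99.9% |
| 15 | 116/135 (0.049) | 3 of 15 | 119/135: 6 of 15 | 116–128 | 99.7% | 98% |
| 10 | 121/140 (0.032) | 3 of 10 | 123/140: 5 of 10 | 121–128 | 90% | 74% |
| 7 | 123/143 (0.041) | 2 of 7 | 126/143: 5 of 7 | 123–128 | 69% | 44% |
| 3 | 126/147 (0.048) | 1 of 3 | 129/147: passes all-failure | 126–128 | 29% | 12% |

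The share is P(min ≤ X ≤ 128)/P(X ≥ min), with X binomial on the completers and min the lowest passing count.

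**Random draw at the goal.** Each missing subject succeeds with probability 0.80. The chance that a draw loses significance is P(Bin(m, 0.80) < 129 − x).

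- 15 missing, x = 116 to 121: 60%, 35%, 16%, 6%, 2%, 0.4%.
- 18 missing, x = 114 to 119: 50%, 28%, 13%, 5%, 2%, 0.4%.

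This does separate fragile from robust results, but at one assumed failure rate (20%) and by chance.

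**Hot deck.** One draw at the observed failure rate loses significance with probability 0.355 at 116/135, 0.005 at 119/135, 0.224 at 114/132 and 0.016 at 116/132. It assumes that missing subjects fail like observed ones, and the plan reports only a combined P-value.

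**MAE for contrast.** 16.6% of 150 is 24.9, taken as 25. P(X≤71 | 150, 0.56) = 0.020 and P(X≤72) = 0.030. So 71 − 25 = 46 MAEs can be added and the 47th loses significance. In completed cases, starting from 22 events, 62 − 22 = 40 can be added with n=132, or 63 − 22 = 41 with n=135. All of these exceed the 15 to 18 subjects expected to be missing even at one year.

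**The case against.** The best case against has five parts.

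- **The number can be derived.** Given observed successes and the number missing, a reader can subtract from 129. True, but that shows the fix is cheap; it does not put the number in the planned output.
- **The endpoint is already well covered.** All-failure and all-success bound every pattern of missing outcomes, and the random draw discriminates. This stands as a limit on weight: the bounds are planned, and only the point between them is not located.
- **An effectiveness version may have been intended.** The opening sentence is general, and imputed data sets exist only for effectiveness. That is plausible, but the text still gives no effectiveness steps, and the mismatch needs correcting either way.
- **Missing data may be fewer than 15 to 18.** The plan says 10% or less, and subjects with a recorded rupture, conversion or qualifying secondary procedure are known failures, not missing. This stands. With few missing the gain is small, because all-failure then passes for most passing results.
- **The weighted z-test may replace the exact test.** If sites are heterogeneous (P<0.15, section 10.5), the Fleiss method applies and a count against 129/150 no longer mirrors the primary test. This is a fair qualification, but the exact test is what the plan itself uses for tipping points, and it is adequate for one supportive table.

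**Conclusion.** The concern holds. As written, the tipping-point rule cannot measure sensitivity to missing data, and the endpoint exposed to missing data has no such rule. Neither primary test changes.

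At the expected 15 missing, a completer result that just passes is overturned by 3 missing failures and one near the planned rate by 6. The planned bounds cannot tell these apart in 99.7% of passing results at a true 88%, or 98% at 90%.

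The figures assume 150 subjects in the ITT set, outcomes that are either known or wholly missing, and the exact test. The importance falls with the amount missing, to 29% and 12% of passing results with 3 missing. This should be corrected, as a supportive analysis.

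**What to change.** Replace the tipping-point paragraph in section 10.2 with one for Treatment Success in the ITT set.

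1. Start with all missing one-year outcomes as successes and convert them to failures one at a time.
2. At each step run the exact binomial test against 0.80 at one-sided 0.05.
3. Report the number and proportion of missing subjects failing at which P first reaches 0.05 or more, beside the observed failure rate. State that the scan uses the exact test even if the weighted z-test is the primary one.
4. Keep the other planned sensitivity analyses.
5. If the MAE count is kept, remove the reference to imputed data sets, run it once in ITT and once in completed cases, and label it a robustness count, not a missing-data analysis. Check it against the FDA request first.

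The cost is one paragraph and a short table from two counts, with no new data. Revision 11.6 is dated April 2018, and section 8.6 shows that two-year data had been reported by October 2016. The scan must therefore be labelled post hoc if it is added after one-year outcomes were seen.
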